2.1 Specific Aims

In the proposed work we aim to:

- **Aim 1:** Test the efficacy of the HOPE-Genomics intervention in improving patient knowledge of genomics (recall rates)
 - Hypothesis:* The use of HOPE-Genomics will result in higher rates of patient knowledge (recall rates) of genomics and their personal test results
 - Strategy:* We will conduct a randomized controlled trial of HOPE-Genomics as an educational tool among patients receiving WES/WGS as a part of their clinical care.
- **Aim 2:** Test the efficacy of the HOPE-Genomics intervention in improving patient receipt of guideline-concordant care
 - Hypothesis:* The use of HOPE-Genomics, will result in higher rates of uptake of evidence-based genetically-guided care vs. usual care.
 - Strategy:* We will conduct a randomized controlled trial of HOPE-Genomics among patients who receive WES/WGS as a part of their clinical care.

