4.0 STUDY PROCEDURES

4.1. Informed Consent and Baseline Survey

Potentially eligible patients will be approached by study team members for verbal informed consent, either by mail/ email, during clinic visits, or by phone. Patients will receive a study packet that will contain an invitation letter, interest postcard, return envelope, and informed consent document. Patients will be randomized into one of three arms immediately after enrollment. Arm 1 is usual care, Arm 2 is return of results only in the HOPE-Genomics tool, and Arm 3 is return of results plus pretest education in the HOPE-Genomics tool.

Arm 1 patients will receive

a pamphlet (20430 Educational Brochure in iRIS) about WES after they enroll. Their clinician will return their genomics test results in a typical manner, without the assistance of the HOPE-Genomics tool.

Arm 2 patients will receive their genomics test results both from their clinician and from the HOPE-Genomics tool but will only view the tool after their results are available. Arm 3 patients will view the HOPE-Genomics tool (containing educational content) before their sequencing results are available. These patients will also receive their genomics test results both from their clinician and from the HOPE-Genomics tool. After completing all study surveys at 9 months post results disclosure, participants in Arm 1 (usual care), will receive access to the HOPE-Genomics tool, which will contain both the educational information and the personalized genomics results.

Table 1: Outcome and covariate data collection

			Patient surveys			MRA
	Baseline	Pre-edu. survey	T1	T2	T3	
Genetic Care outcomes						
MD recommendations						
Screening, surgery, meds			X	X	X	X
Referrals GC, specialists			X	X	X	X
Cascade testing			X	X	X	X
Patient utilization/behavior						
Screening, surgery, meds			X	X	X	X
Consult GC, specialists			X	X	X	X
Inform family members			X	X	X	
Cascade testing			X	X	X	
Patient-centered outcomes						
Recall of results	X		X	X	X	X
Understanding of results			X	X	X	
Genomic knowledge	X	X	X	X		
Engagement in care			X	X	X	
Information seeking				X		
Psychosocial impact	X		X	X	X	
Follow up outcomes						
HOPE-Genomics usability			X	X		
Satisfaction with MD-patient communication and care			X	X		
Covariates						
Socio-demographics	X					X
Clinical information						X
Other (e.g., health literacy)	X					X

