4.1.2 Patient Follow Up Survey

The follow up surveys will either be mailed to the participant, along with a return envelope, provided electronically and/or by text message via REDCap survey link, or completed via phone or Zoom call with a staff member, according to patient preference. For patients who opt to complete their follow-up surveys via phone or Zoom call, study staff will not assist them in selecting the correct answers for questions pertaining to their understanding of cancer and genetics. Study staff will follow-up with patients once a week within 2–3-week window to encourage completion of the survey. We will attempt to contact non-responders up to five times to encourage survey participation.

Understanding of personal genomic knowledge will be assessed through an adapted version of a measure created by Freedman and colleagues¹, which evaluated women's knowledge of their personal cancer ER and HER2 status using a two-item question (3 response options; yes/no/I don't know). Our adapted questions will evaluate patients' recall of genomic testing results and the implications of their results (i.e., harmful and unknown). Patient recall will be assessed at all survey timepoints (i.e., at baseline, 10 days, 3 months and 9-months following results disclosure with a clinician).

Engagement in care will be assessed by a novel item that queries patients as to whether WES prompted questions to care providers (yes, no, don't know). We will use items adapted for our CSERII study to ask patients if they recall changes to their cancer treatment as a result of their genomic test results. We will also assess engagement via interactive functionality of HOPE-Genomics (see below). Seeking and sharing information about genetic tests will be assessed using two items from the Health Information National Trends Survey (HINTS) 4 that were adapted for our CSERII study.⁷

Satisfaction with physician/patient communication around the results of gene testing will be assessed with a 7-item measure adapted from HINTS 3 & 4. Satisfaction with care will be assessed using a single item measure from Charles and colleagues that was created to evaluate satisfaction with genetic counseling and that was adapted for our CSER1 study.¹⁴ We have also included two novel questions to assess whether patients (1) recalled asking their healthcare providers about their genetic test results and (2) recalled receiving a copy of their genetic test report.

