6.0 DATA ANALYSIS

As noted in Section 4.0, we are administering the survey items in order to help with item reduction for the trial. We will generate descriptive statistics (e.g., distributions, means) in order to evaluate for ceiling and floor effects. An amended survey will be submitted prior to administration.

Primary outcome (i.e., patient knowledge, recall rates) will be assessed at the 10-day post-disclosure timepoint.

We will be using MRA and survey data to evaluate if participants received contextual guideline-concordant care. This will involve review of receipt of prophylactic surgery, chemoprevention, targeted therapy for germline mutations, consultation with genetic counseling/ genetic specialists, informing family members, and family member cascade testing. To generate concordance scores for patients already on active therapy, patients will be asked about their current and/or planned cancer treatment at baseline and at each follow-up timepoint in the study (i.e., chemotherapy, radiation therapy, cancer-directed surgery, hormone therapy, immunotherapy, and targeted therapy). Patients will be considered as being contextually guideline-concordant if they receive at least 75% of the recommended guidelines. In sensitivity analyses, we will vary the cutoff for guideline- concordance between 50% and 100%. Survey data will also be used to evaluate usability of the HOPE-Genomics application, the psychosocial impact of using the tool, engagement in care, genetic knowledge, and understanding of genomic test results

6.1 Sample Size and Accrual Rate:

We plan to anchor our cohort on patients with somatic testing. We expect to accrue 465 patients: 155 per each arm. We assume that there will be a 10% attrition rate among accrued patients, leaving us with a final analytical sample of 390 patients. For the first 3 months, we assume that 17 patients are enrolled each month, during which time we will evaluate and optimize study processes. After this we will increase monthly accrual to 35 patients. We expect to be complete with accrual in 16 months. Patient participation will be approximately 7 months consisting of baseline pre-testing followed by genetic testing/results disclosure and then post-testing. The estimated total study time including analysis will be 26 months.

6.2 Statistical Analysis Plan:

The study data will consist of three main areas:

- 1) patient knowledge testing and clinical care recommendations via survey-based questions

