6.2.2 Secondary Outcome

In Aim 2, we will assess the effect of the intervention on the proportion of patients with contextual NCCN guideline-concordant care. This approach is modeled after analyses used by [name] et al. in the MedSeq CSER1 project.^{25,26} Operationalization of contextual guideline concordant care: In the primary analysis, we will assess the uptake of contextualized guideline-concordant care taking into account clinically relevant, patient specific circumstances. We will use clinical characteristics from the

EHR to assign each patient to clinical category for which there are discrete NCCN recommendations. Using patient self-reported baseline/T1 and EHR data, following sequencing disclosure, we will create a summary genetically guided care variable ranging from 0-100%. The denominator consists of the total number of contextual guideline-concordant interventions/behaviors possible during a 12-month period following results disclosure for any given patient given his/her germline findings, family history, and clinical characteristics. The numerator consists of the total number of patient-adopted guideline concordant intervention/behaviors completed during a 12-month period following results disclosure. For a patient found to have a pathogenic germline/actionable somatic variant, we will assign benchmarks of genetically guided care derived from evidence based clinical practice guidelines (i.e. NCCN, United States Preventive Services Task Force, or medical society based clinical guidelines). We convene a weekly POTB meeting where a panel of medical geneticists, cancer geneticists, genetic counselors, genetic nurse practitioners, oncologists, gastroenterologists, cardiologist, and hepatologist review cases and develop multidisciplinary contextualized guideline concordant recommendations (chaired by [name]).

In the secondary analyses, we will define guideline concordant as meeting $\geq 75\%$ of recommended guidelines. In sensitivity analyses, we will vary the cutoff for guideline concordance between 50% and 100%.

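### Aim 2 care uptake merges unblinded self-report with record data, and no planned analysis separates the two, so a reporting difference between arms could be read as a care difference

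*Combined protocol and SAP*

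**What the plan says.** Section 6.0 gives the Aim 2 data source: "We will be using MRA and survey data to evaluate if participants received contextual guideline-concordant care". The components it lists include "informing family members, and family member cascade testing".

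Section 6.2.2 builds the score: "Using patient self-reported baseline/T1 and EHR data, following sequencing disclosure, we will create a summary genetically guided care variable". It then defines the count: "The numerator consists of the total number of patient-adopted guideline concordant intervention/behaviors completed during a 12-month period following results disclosure".

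Table 1 in section 4.1 has a block labelled "Patient utilization/behavior". In it, screening/surgery/medication and counselling/specialist consultation carry marks at T1, T2, T3 and MRA. Telling relatives and cascade testing carry marks at T1–T3 but not under MRA. Section 4.6, however, names both of these among the data to be abstracted from the record.

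The Aim 1 hypothesis in section 2.1 is: "The use of HOPE-Genomics will result in higher rates of patient knowledge (recall rates) of genomics and their personal test results".

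The Aim 2 checks are a concordance cutoff varied from 50% to 100% (6.0, 6.2.2), linear regression on the same 0–100% score (6.2.3), and three any/none care categories (6.2.3).

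**The concern.** Aim 2 is meant to show whether the tool changes the care patients receive. Part of its score is what patients say they did, and patients know whether they used the tool or were given a pamphlet. The tool is designed to change what patients know about genomics and recall of their results. It is plausible, though not documented, that this also changes how accurately they report genomics-related care. If so, two arms with identical care could score differently.

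The plan has no rule for disagreement between survey and record, no validation of self-report and no record-only analysis. Moving the cutoff or switching to linear regression reuses the same mixed numerator. The any/none categories split the score by type of care, not by data source. A significant Aim 2 result could therefore not be attributed to care rather than reporting.

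**Working it through.** **Plan's own figure.** The documents give no power for Aim 2, so the test formula was checked on Aim 1 (6.2.1): 39% vs 54%, 130 vs 260, two-sided 5%. The pooled rate is (130×0.39 + 260×0.54)/390 = 0.49. The SE under the null is √[0.49×0.51×(1/130+1/260)] = 0.0537, and under the alternative 0.0528. Power = Φ[(0.15 − 1.96×0.0537)/0.0528] = 80.2%, which matches the stated 80%.

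**Inputs for the illustration.** From the documents: 130 vs 260 (Aim 1's analytical sample), the 75% cutoff and two-sided 5%. Assumed, because the documents do not give them:
- four recommended items per patient, independent, with true completion p = 0.70 in every arm;
- MRA sensitivity m = 0.70 or 0.85;
- Usual Care self-report sensitivity s = 0.60 or 0.75, higher by a fixed gap in Arms 2/3;
- no false reports, and every patient scorable.

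**Formulas.** Probability that an item is credited:
- dual-source, either source counts: p[1 − (1−m)(1−s)]
- dual-source, MRA overrides: p·m
- survey-only: p·s

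A patient is concordant with at least 3 of 4 items credited (75%). The concordance rates are compared with the same two-proportion test.

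**One case in full** (m = 0.70, s = 0.60 vs 0.70, two dual-source and two survey-only items, either-source credit):
- dual-source items: 0.7×(1 − 0.3×0.4) = 0.616 vs 0.7×(1 − 0.3×0.3) = 0.637;
- survey-only items: 0.42 vs 0.49;
- P(at least 3 of 4): 33.5% vs 41.1%, a false difference of 7.6 points;
- SEs 0.0523 (null) and 0.0514 (alternative);
- rejection rate Φ[(0.0760 − 1.96×0.0523)/0.0514], about 30%, with a negligible lower tail.

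**False-positive rate over the four m, s combinations, p = 0.70:**

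| Source structure | 5-point gap | 10-point gap | 15-point gap |
|---|---|---|---|
| Two items survey-only, either source counts | 10–11% | 26–32% | 51–61% |
| Two items survey-only, MRA overrides on the others | 8–9% | 18–20% | 34–39% |
| MRA on all four, either source counts | 5–6% | 7–11% | 8–19% |

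At 50% true completion, the first row becomes 7%, 13–15% and 24–28%. With no gap, every row is 5%.

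**Two further checks at the 10-point gap, first row.** If only 40% of patients were scorable (assumed; 52 vs 104), the rate is 13–16%. If Arms 2/3 also made fewer false reports (5% vs 20% of items not done, assumed), the spurious difference is within 1 point of zero at 70% completion, and about 6–7 points against the tool at 50%.

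**The case against.** Much of the case on the other side stands.

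- **Source of the family items.** Section 4.6 lists telling relatives and cascade testing as abstracted data. If 4.6 governs rather than Table 1, the third row of the table applies and the exposure is small.
- **Timing.** Section 6.2.2 names only baseline and T1 self-report. T1 is about 10 days after results reach the EHR, and results reach the tool 3–14 days after the EHR (4.4). Read literally, self-report could credit little of a 12-month window. Section 6.0 and Table 1 can be read more widely, so the documents do not settle it.
- **What recall means.** A reader might infer that the tool is documented to improve memory of care. It is not: section 2.1 speaks of genomics and personal test results, and 6.2.1 defines recall as correctly recalling somatic results. The survey item used "to ask patients if they recall changes to their cancer treatment as a result of their genomic test results" belongs to engagement in care (4.1.2), and nothing says it feeds the Aim 2 score. The 15-point recall gain in 6.2.1 is therefore not evidence of a 15-point gain in care reporting.
- **Direction.** A reader might infer that the bias must favour the tool. That holds only if patients never over-report; with fewer false reports in Arms 2/3 it can vanish or reverse.
- **Partial handling.** Section 6.2.3 already analyses sharing with relatives outside the composite, and section 2.0 gives family sharing as a tool function, so a difference there may be real.

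None of this supplies a record-only analysis or a precedence rule.

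**Conclusion.** The plan combines unblinded self-report with record data in the Aim 2 score, and no planned analysis isolates the source. A reporting difference could therefore appear as a care difference. Neither its direction nor its size can be learned from the documents.

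The illustrative rates at a 10-point gap (about 26–32%, 18–20% and 7–11%, against a nominal 5%) depend on assumed item counts, completion rates, sensitivities, absence of false reports and use of the full Aim 1 sample. They show only that the answer depends heavily on which items have a record source and on how the sources are combined, and the plan settles neither.

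A reader might go further and conclude that the composite should be replaced by an MRA-only score. The documents do not support that as a clear improvement. It would remove telling relatives and cascade testing from an outcome that sections 6.0 and 6.2.2 define to include patient behaviours. It would also rest on equal record sensitivity across arms, which cannot be taken for granted because clinicians of intervention patients can also view results in the tool (4.4). A pre-specified sensitivity analysis is what the evidence justifies.

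**What to change.** 1. Keep the combined score as the planned Aim 2 outcome. In 6.2.2, pre-specify an MRA-only sensitivity analysis of the between-arm comparison. Restrict numerator and denominator to the patient-behaviour items with an MRA mark in Table 1: screening/surgery/medication and counselling/specialist consultation.
2. State that an Aim 2 difference will be interpreted as a change in care received only if the MRA-only estimate points the same way. Otherwise describe it as possibly due to reporting.
3. Label telling relatives and cascade testing as self-reported wherever they rest on surveys alone.
4. Reconcile Table 1 with section 4.6 on whether those two items are abstracted, and section 6.2.2 (baseline/T1) with Table 1 (T1–T3) on which surveys feed the score.

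Cost: SAP wording and one more run on data already being abstracted. Enrolment, intervention and Aim 1 are untouched. The downside is that care outside the institution is missed in the record, which costs precision. The analysis also assumes similar record sensitivity across arms, and this should be stated as a limitation.

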4.1.1 Patient Baseline Survey

At time of consent, patients will complete the baseline survey. Baseline survey outcomes are detailed in Table 1. We will follow standard survey methods as outlined by Dillman^{2,3} (e.g., contact type and intervals; mail/email/in-person reminders) to ensure high response rates. The survey will be administered in one of the following ways, according to patient preference: (1) mailed to the participant, along with a return envelope, (2) provided electronically and/or by text message via REDCap survey link, or (3) completed over a scheduled phone or Zoom call with a study staff member. For patients who complete the baseline survey via phone or Zoom call, study staff will not assist them in selecting the correct answers for questions pertaining to their understanding of cancer and genetics.

Germline sequencing knowledge will be measured using an adapted version of the UNC Genomics Testing Knowledge Scale¹, a validated 25-item measure developed by Langer and colleagues to evaluate overall understanding of genomics and health. We will also assess patients' knowledge of the implications of WES on 1) personal cancer risk, 2) family cancer risk, and 3) genetics generally.

General cancer genomics knowledge will be assessed using a modified form of a 12-item measure developed by Blanchette and colleagues.⁵ The measure assesses three domains of cancer genomic knowledge: 1) general understanding of cancer, 2) how biological changes influence cancer, and 3) the potential implications of genomic testing in cancer. Higher general cancer genomic knowledge has been associated with higher levels of education, higher personal income and patients' perceived ability to provide informed consent for genomic testing.

Knowledge about the use of genetic testing in cancer will be assessed using a 6-item measure developed by Roth, Gray and colleagues for the Lung-MAP study (unpublished). The measure assesses participant's knowledge of why genetic testing is used in cancer care (e.g., to help select a treatment, to predict response to treatment). Eight items have been added in the following content areas: 1) use for cancer staging, 2) use to time cancer onset, 3) use to predict treatment efficacy, 4) use for clinical trials, 5) use to monitor cancer treatment, 6) use to identify a cancer's location, 7) use to determine metastasis, and 8) use to assess cancer risk.

Knowledge about the difference between somatic and germline testing (categorical questions) will be assessed using a 7-item measure developed by Roth, Gray and colleagues for the Lung-MAP study (unpublished). The measure assesses participant's knowledge about 1) germline mutations found every cell of the body and 2) somatic mutations found only in cancer cells.⁶ 4 items have been added in the following content areas: 1) finds gene changes that a person was born with, 2) finds gene changes that have happened over a lifetime, 3) finds gene changes that are passed from parent to child, and 5) commonly has health implications for family members.

Understanding of personal genomic knowledge will be assessed through an adapted version of a measure created by Freedman and colleagues¹, which evaluated women's knowledge of their personal cancer ER and HER2 status using a two-item question (3 response options; yes/no/I don't know). Our adapted questions will evaluate patients' recall of genomic testing results and the implications of their results (i.e., harmful and unknown). Patient recall will also be assessed 10 days, 3 months and 9-months following results disclosure with a clinician.

Recall of prior genetic counseling will be assessed with a single question (3 response options; yes/no/I don't know) created by Sheppard and colleagues, which evaluated African American women's experiences with counseling counselling for hereditary breast cancer.²

Psychosocial wellbeing/anxiety/depression/stress will be assessed at baseline and at each follow-up timepoint using a 14-item measure from Zigmond's Hospital Anxiety and Depression scale.³ These questions will assess potential changes in patients' psychosocial wellbeing in response to genetic testing and their experience with cancer throughout the randomized trial.

Socio-demographics will be assessed using questions (including race, ethnicity, marital status, education) from the Centers for Disease Control and Prevention's Behavioral Risk Factor Surveillance System (BRFSS) questionnaires. The BRFSS questionnaires are health-related telephone surveys that collect state data about U.S. residents regarding their health-related risk behaviors, chronic health conditions, and use of preventive services.⁴ Primary language spoken will be assessed by a 4-item measure developed for CSERII. Sex, gender, and date of birth will be assessed using measures from CSERII.

Other covariate data (e.g., health literacy, numeracy, health status, and primary language spoken) will be assessed using validated measures.

- Health literacy will be assessed by up to 3 single-item health literacy screening questions, as evaluated by Chew and colleagues.⁵
- Numeracy will be assessed by a 3-item version of the Subjective Numeracy Scale (SNS-3), as validated by McNaughton and colleagues.¹⁷
- Health-related Internet use will be assessed by a an adapted 1-item measure from the National Cancer Institute Health Information National Trends Survey (HINTS).^{18,19}
- Health status will be assessed by a validated single item measuring general self-rated health.^{18,20,21}
- Patient-reported functional status will be measured by a single item measure developed by Basch and colleagues (patient ECOG-PS).²²
- Quality of care will be assessed using a single item measure from HINTS.⁶

